**Sensitivity analyses**

For all the sensitivity analyses the reference standard is the local FFA and the index tests use the collapsed definition using all valid index test results as per analysis A1 in table 3.

A sensitivity analysis will use OCT from the reading centre (rather than local OCT) as the index test and calculate the diagnostic performance of OCT and the paired comparisons between the reading centre OCT and the other index tests (sensitivity analysis 1).

Sensitivity analyses will explore the impact of varying the test cut-off for relevant tests (varying positive test definition of the patient’s subjective assessment to “worse” – sensitivity analyses 2, and of the visual acuity test to 20 letters –sensitivity analysis 3 and of a visual acuity drop of 10 letters or more from last FFA confirmed false positive – sensitivity analysis 4) to explore possible threshold effects.

Sensitivity analysis 5 will define indeterminate FFA as positive and sensitivity analysis 6 as negative, instead of the default position of missing. Sensitivity analyses 5 and 6 will only be undertaken if there are a substantial number of indeterminate results (minimum of 10%).

The sensitivity analyses described apply only to the primary person level analysis (analyses A) and will not be carried out for the GEE model.

For the survival analysis the impact of changing the assumption of the date of participants developing nAMD will be tested. In the default analysis this will be the date of the FFA confirming nAMD. In the sensitivity analysis this date will be altered to a time halfway between the positive FFA and the previous negative FFA.

The sensitivity analyses are listed in the table below:

Reference standard definition: A = Local FFA. Collapsed definition. Reference standard is positive if local FFA is converted at any time point and negative if it is not converted throughout.

Index test definition: A = Collapsed definition. Positive if there is any prior positive index test and negative if the index test is negative throughout. All index tests are used.

**Table 4 Description of sensitivity analyses**

S.A. number	Analysis	Reference standard definition of disease	Index test definition
1	Uses OCT from the reading centre. Diagnostic performance of OCT and a paired comparison of the OCT and the other tests	A	A: reading centre OCT
2	A positive subjective vision is defined as “worse” or “much worse”. Diagnostic performance of subjective vision and a paired comparison of subjective vision and the other tests	A	A: Subjective vision “worse” or “much worse”
3	A positive visual acuity is a change of 20 letters or more. Diagnostic performance of visual acuity and a paired comparison of visual acuity and the other tests.	A	A: Visual acuity change of 20 letters or more
4	A positive visual acuity is a change of 10 letters from the last FFA confirmed false positive. Diagnostic performance of visual acuity and a paired comparison of visual acuity and the other tests.	A	A: Visual acuity change of 10 letters or more from the last FFA confirmed false positive
5	Indeterminate FFA and indeterminate index tests taken as positive. Diagnostic performance of the individual tests and a paired comparison of sensitivity and specificity between the tests.	A: indeterminate results defined as positive.	A: indeterminate results defined as positive.
6	Indeterminate FFA and indeterminate index tests taken as negative. Diagnostic performance of the individual tests and a paired comparison of sensitivity and specificity between the tests.	A: indeterminate results defined as negative.	A: indeterminate results defined as negative.

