#### **Reading centre**

An ophthalmic reading centre (Central Angiographic Resource Facility) located at Queen's University Belfast will independently undertake grading of anonymised images (FFA, OCT, fundus photography, autofluorescence- optional) acquired at all the timepoints highlighted in table 1.

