### **Time points of outcome collection**

In order to assess the sensitivity and specificity of the diagnostic tests under evaluation, each of the diagnostic tests being assessed will be performed on the study eye at each routine clinic visit during the period of follow up.

Results from the diagnostic tests according to the definitions will be recorded on a standardised case report form. If any diagnostic tests are positive this will trigger the request for an FFA and the absence/presence of nAMD (and classification) will be recorded. These data will be uploaded to the study website by study staff.

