**Table 1 Timing of outcome collection**

Assessment	Recruitment	Routine visits (approx. every 8 weeks)	If any diagnostic test positive	If FFA positive	18 months	exit
Assessment of eligibility criteria	✓					
Written informed consent	✓					
Baseline vision and risk factors	✓					
Blood collection	✓			✓		✓
Diagnostic tests: 
 
• Subjective patient vision
 
• AMSLER
 
• Visual acuity
 
• OCT
 
• Fundus examination
 
• Autofluorescence (only if available)
 
	✓	✓			✓	✓
Reference standard: FFA	✓		✓		✓	✓
Post conversion case note review						✓
Upload of required imaging to reading centre for analysis	✓		✓		✓	✓

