### **Index test result definition for analysis A**

For each index test, multiple test results will be collapsed into a single test result. Any positive test result over the valid follow-up period will be classed as an overall positive result. To be a negative index test result, all index test results must be negative. The classic 2x2 table for assessing diagnostic accuracy with our definitions is provided in Table 2 below.

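### Sensitivity analysis 1 pairs reading-centre OCT, graded only at selected visits, with local tests recorded at every visit, so its specificity may be overstated by 0 to about 5.4 points

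*SAP*

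**What the plan says.** The SAP section on sensitivity analyses sets one rule for all of them: "the index tests use the collapsed definition using all valid index test results as per analysis A1 in table 3". Sensitivity analysis 1 changes only the source of the OCT reading. Table 4 describes it as "Uses OCT from the reading centre. Diagnostic performance of OCT and a paired comparison of the OCT and the other tests", gives its index definition as "A: reading centre OCT" and places no restriction on visits.

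The collapsing rule for analysis A is: "Any positive test result over the valid follow-up period will be classed as an overall positive result". A negative requires every available result to be negative.

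For the local tests, the SAP section on time points says that "each of the diagnostic tests being assessed will be performed on the study eye at each routine clinic visit during the period of follow up".

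The reading centre has a narrower schedule. In SAP Table 1 the row "Upload of required imaging to reading centre for analysis" is ticked under recruitment, any positive diagnostic test, 18 months and exit. The routine-visit column has no tick. Protocol Table 1 has the same pattern, with 3 years in place of exit. Protocol section 6.3 says that the reading centre grades images "acquired at all the timepoints highlighted in table 1".

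Neither document limits the comparator tests to graded visits or says how ungraded visits count. SAP Table 2 classes a participant as index-negative on whatever prior time points are available, so ungraded visits drop out without comment. The dummy table for this analysis pairs reading-centre OCT with visual acuity, Amsler, fundus evaluation and subjective vision. It has no row against local OCT.

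**The concern.** Under an any-positive rule, a non-converter's chance of a false positive grows with the number of readings. A participant who never triggers an FFA has a full series of local results but only two follow-up reading-centre OCT grades, at 18 months and exit. Any further grades exist because a local test was positive.

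The gap is not random. If the trigger rule is followed, the ungraded visits are exactly those where all local tests were negative. The comparators have no positives to lose there, whereas reading-centre OCT might have been called positive and cannot be. Outside the two scheduled visits it can add a positive only where a local test already had one.

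A McNemar comparison of specificity from this analysis could therefore favour reading-centre OCT partly because of how images are sent for grading. It would be the only planned result in which independently graded OCT serves as an index test.

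**Working it through.** **Plan's own figure (background).** The SAP sample size section uses discordance 0.30, a sensitivity difference of 0.15, two-sided 5%, 90% power and 28% incidence. McNemar: [1.96·√0.30 + 1.2816·√(0.30 − 0.15²)]² / 0.15² = 135.9, so 136 converters. Then 136/0.28 = 486, against 491 stated. 491/(1 − 0.12) = 558, against 560 stated. Both agree closely, and neither is in dispute. The same section states a 7-point detectable difference in specificity (94% to 87%). I use it only as a scale.

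**Visits, K.** Protocol section 3.2 gives 4 to 8 weekly visits in year 1 and 8 to 12 weekly in year 2. I assume that year 3 is like year 2.
- Fewest: 52/8 + 104/12 = 15.2.
- Most: 52/4 + 104/8 = 26.
- Eight-weekly throughout: 156/8 = 19.5.

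I use K = 15, 19 and 26. Two of the K visits are graded by schedule.

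**Model for a non-converter (assumptions).** Visits are independent. Reading-centre OCT has the per-visit false-positive rate that gives 94% if every visit is graded: f = 1 − 0.94^(1/K). The four other local tests are independent, each 87% after collapsing: g = 1 − 0.87^(1/K). A share c of reading-centre false positives coincides with a local OCT positive. The documents do not give c, so I run it from 0 to 1.

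The probability that a reading-centre positive falls on a visit with some local positive is q = c + (1 − c)·[1 − (1 − g)^4]. At c = 0, q = 1 − (1 − f)(1 − g)^4. With a the proportion of local positives that lead to an FFA and upload:

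collapsed specificity = (1 − f)² · (1 − f·q·a)^(K−2)

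**Worked case, K = 19, c = 0.5, a = 1.** f = 0.00325, g = 0.00730, q = 0.514 and f·q = 0.00167. Then (1 − f)² = 0.9935, (1 − 0.00167)^17 = 0.972, and the product is 0.966, which is 2.6 points above 94%.

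**Full trigger adherence (a = 1):**

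| Coincidence c | K = 15 | K = 19 | K = 26 | Excess over 94% (points) |
|---|---|---|---|---|
| 1 | 94.0% | 94.0% | 94.0% | 0 |
| 0.8 | 95.0% | 95.0% | 95.1% | 1.0 to 1.1 |
| 0.5 | 96.5% | 96.6% | 96.7% | 2.5 to 2.7 |
| 0 | 99.0% | 99.2% | 99.4% | 5.0 to 5.4 |

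**Incomplete adherence.** Protocol section 7.3 treats an FFA request rate below 50% after a positive test as futile, so 50% is a natural lower limit. At a = 0.5 the excess runs from about 2.6 points (c = 1) to 5.5 (c = 0).

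**Does filtering the comparators to graded visits help?** An 87% comparator becomes (1 − g)²·(1 − g·a)^(K−2). At a = 1 this is 0.87 exactly, so nothing changes. At a = 0.75 it is about 90%, and at a = 0.5 it is 92% to 93%. Under full adherence the filter removes none of the comparator's positives, and the selection of graded visits remains.

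**Sensitivity.** A converter's triggered visit is itself uploaded, so most detections are kept. What can be lost is an earlier reading-centre positive at a visit where all local tests were negative. I expect this effect to be smaller and have not put a figure on it.

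**The case against.** The strongest reply is that the trigger rule largely protects the comparison. Every visit with a local positive should lead to an FFA and an upload, so local OCT false positives do reach the reading centre. If reading-centre positives almost always coincide with local ones, the excess is close to zero. That stands, and it is why the range starts at 0. It rests on agreement that the documents do not report.

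A reader might infer a much larger effect by setting 2 readings against 19.6 visits for an 87% test: 0.87^(2/19.6) = 98.6%, a gap of 11.6 points and above the 7-point yardstick. The documents do not support that reading. It leaves out the triggered uploads in Table 1. It also starts from 87%, although the SAP says that its reference values are those observed for OCT, most naturally the 94%. From 94% the same crude sum gives 99.4%, a gap of 5.4 points, below the yardstick.

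A reader might also infer that reading-centre OCT is bound to look more specific, or that the analysis cannot inform on expert reading at all. Neither follows: the excess can be nil, and the SAP says only that reading-centre OCT replaces local OCT, without stating a question about reader effect.

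It is also fair that this is one of six sensitivity analyses and that it keeps the whole-follow-up definition deliberately, to stay a variation on A1. That limits the importance of the point but does not resolve the mismatch.

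**Conclusion.** The mismatch is certain from the documents: an all-visit definition is applied to a test that is graded only at recruitment, triggered, 18-month and exit visits. The consequence is conditional. With full trigger adherence, reading-centre OCT specificity may be overstated by 0 to about 5.4 points for a 94% test. The size rests on reader agreement, independence between visits and the assumed accuracy of the other tests. Any-time sensitivity may be slightly understated.

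The statement that ungraded visits are all-negative has exceptions. An FFA after further acuity loss is at the clinician's discretion once a triggered FFA has been negative (protocol 3.2.3), triggers may be missed, and a conversion may be found on an FFA done for the first eye (protocol 3.6.6).

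It would be wrong to extend the point to the main results. A1 to A3 and A7 use local OCT. A4 to A6 change the reference standard to the reading-centre FFA but do not use reading-centre OCT as an index test. The change is worth making before analysis, but no primary conclusion depends on it.

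**What to change.** In sensitivity analysis 1, replace index definition A with index definition C, which the SAP already uses for A3 and A6: the result at the last available visit, within 3 months of the last FFA. Apply it to reading-centre OCT and to every comparator, at visits that have a reading-centre OCT grade. For non-converters who complete follow-up this is normally the exit visit, which is uploaded by schedule and not because a test was positive.

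Add a paired comparison of local with reading-centre OCT on those same graded visits, with a row in the dummy table. This is the comparison that isolates the reading itself.

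If the definition A version is kept, label it as not like for like because grading is selected on local positivity. State that restricting the comparators to graded visits does not remove this bias. Some selection also remains under definition C where a participant's last FFA was a triggered one, and should be reported as a limitation.

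The cost is SAP wording, a filter on visits and one extra table row, with no new data. The analysis will have fewer readings per participant and will depart from the whole-follow-up monitoring definition used in A1.

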## **Analysis Objective 1: Determine the diagnostic monitoring performance of the interventions**

### **Analysis A. Person level diagnostic accuracy analysis.**

**Table 3** outlines the different definitions for the reference standard and an index test positive result for all the analysis under the person level diagnostic accuracy analysis.

Under the main analysis approach (analysis A1, see **table 3**), repeated monitoring test assessments are collapsed over time to give a single candidate test result (positive or negative). This is compared with a single final local FFA result from the participant. Other approaches will be considered by varying the definitions for reference standard and index tests included in the analysis (analysis A2 – A7, see **table 3**).

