### **Participant inclusion criteria for analysis A**

For each of the 5 index tests, the following criteria will be applied separately:

1. Last FFA result shows no nAMD:

The participant will be included if there is **at least one prior** index test result during the follow-up period.

2. Last FFA result shows nAMD:

The participant will be included if there is an index test result within the previous 3-months. If a participant does not have an index test result within the previous 3-months of their last FFA the FFA will not be considered valid and we will look for an earlier FFA result for the participant and apply rules 1 and 2 again on the earlier FFA.

If no follow-up FFA is available which satisfies either criteria, then the participant will be excluded. If no follow-up FFA is available, the participant will be excluded from the analysis.

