**Table 2 Two by two table: definitions of test and disease status.**

	Index positive	Index negative
Reference standard positive: nAMD	True positives Any reference standard indicates nAMD in study eye AND Any index test result is positive during valid follow-up period	False negatives Any reference standard indicates nAMD in study eye AND Index test negative for all available prior time points
Reference standard negative: No nAMD	False positives All reference standard results indicate no nAMD in study eye AND Any positive index test result during valid follow-up period	True negatives All reference standard results indicate no nAMD in study eye AND Index test negative for all available prior time points

Sensitivity and specificity will be calculated with 95% confidence intervals calculated using the Agresti-Coull method (Zhou 2002). Positive and negative likelihood ratios will also be calculated with 95% confidence intervals calculated using the method in Zhou 2002. Diagnostic odds ratios and the proportion of indeterminate tests will be calculated with 95% confidence intervals. A ROC curve will be plotted and the area under the ROC curve calculated using the trapezoidal rule for visual acuity tests. The standard error for the AUC will be calculated using the method of DeLong, DeLong and Clarke-Pearson (1998) and used to form an asymptotic normal 95% confidence interval.

Monitoring sensitivity and specificity of the tests will be compared using McNemar's statistical test (with 95% confidence intervals produced using Newcombe's method) (Newcombe 1998).

For comparing sensitivities under the primary analysis, the McNemar 2x2 table will be constructed using only patients who have had a positive FFA result. They will be classified as having a positive index test, if the index test has any positive results during the valid follow-up period. They will be classified as having a negative index test, if all prior available tests have been negative during their valid follow-up period. For comparing specificities under the primary analysis, the McNemar 2x2 table will be constructed using only patients who have had negative FFA results throughout using the same index test classification.

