**Missing data and indeterminate and unreliable results**

Absence of a positive reference standard during valid follow-up period will be presumed to indicate a negative result.

Indeterminate FFA results: As a default position indeterminate tests will be treated as missing, but there will be sensitivity analyses to test that assumption (see below). For the primary person level analysis (Analysis A1), if the last available reference standard is missing/indeterminate then the previous reference standard will be used. If no reference standards have been carried out after the baseline reference standard or they are all indeterminate/missing then that participant will be excluded from the analysis unless a curtailed period with a valid FFA and index test result exists.

For the prognostic model (Analysis D) the impact of missing covariate data will be assessed and multiple imputation will be used for baseline variables if considered appropriate.

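### As printed, sensitivity analysis 5 relabels eyes with an early indeterminate FFA and a later clear negative FFA as nAMD, shifting the tests' sensitivities by unequal, artificial amounts

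*SAP*

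**What the plan says.** By default the SAP treats an indeterminate FFA as missing. For A1, "if the last available reference standard is missing/indeterminate then the previous reference standard will be used" (Missing data and indeterminate and unreliable results). An early indeterminate FFA followed by a definite one therefore changes nothing in A1: the definite result stands.

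SA5 and SA6 replace that default. The text under Sensitivity analyses describes them as recoding indeterminate FFAs only. Table 4 goes further for SA5: "Indeterminate FFA and indeterminate index tests taken as positive". SA6 is the mirror image, with both taken as negative. Neither place limits the recode to the last FFA. Both analyses are conditional on at least 10% of results being indeterminate; the denominator is not given.

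The reference definition printed for Table 4 is: "Reference standard is positive if local FFA is converted at any time point and negative if it is not converted throughout". Table 2 has the same any-time rule for disease: "Any reference standard indicates nAMD in study eye". So do the opening Method paragraph of the Analysis section and the McNemar construction for specificity, which is restricted to patients negative on every FFA.

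Other wording points to the last FFA. Of the collapsed index result in A1, the SAP says: "This is compared with a single final local FFA result from the participant". The A1 inclusion rules also start from the last FFA ("Last FFA result shows no nAMD" is the first case). The sensitivity analyses inherit from A1: "the index tests use the collapsed definition using all valid index test results as per analysis A1 in table 3".

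**The concern.** SA5 should show how far the conclusions depend on reference results that were never resolved. Under the any-time rule it also overrides results that were resolved. Because study monitoring ends at a clinical diagnosis of nAMD in the study eye (Protocol 3.6.7), an eye still followed after an indeterminate FFA had generally not been diagnosed. A later negative FFA then settles the matter, yet SA5 as printed moves that eye into the diseased group. SA6 leaves the same eye negative, so the gap between SA5 and SA6 reflects resolved and unresolved eyes together.

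The distortion is not common to all tests. A relabelled eye becomes a true positive for each index test that was ever positive in it and a false negative for each test that never was. The plan's main comparison is between tests, by McNemar, so an unequal shift matters more than a common one. Two analysts could also both follow the SAP and obtain materially different SA5 results, depending on which description of the reference standard they use.

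**Working it through.** **Group sizes from the plan.** The sample size sections give 80% v 65% sensitivity, disagreement 0.30, two-sided 5%, 90% power and 28% incidence.

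- McNemar: n = [1.960√0.30 + 1.282√(0.30 − 0.15²)]² / 0.15² = 135.9, so 136 diseased.
- 136/0.28 = 486, about 1% below the stated 491. A simpler variant, (1.960 + 1.282)² × 0.30/0.15², gives 504.
- 491/0.88 = 558, against the stated 560.

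The figure reproduces closely enough. I use 491 × 0.28 ≈ 137 diseased (D) and 354 non-diseased eyes.

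**Effect of relabelling.** Let k be the number of eyes with an earlier indeterminate FFA and a later negative one, s the A1 sensitivity, and q the share of the k eyes positive on that test at any time in the valid follow-up period. With index results not recoded:

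Sensitivity in SA5 = (sD + qk)/(D + k), a change of k(q − s)/(D + k).

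The sign depends only on whether q is below or above s. The documents give no indeterminate rate, so k and q are assumptions.

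**Untriggered 18-month FFA.** Take 10% indeterminate at one non-final FFA per non-converter: k = 354 × 0.10 = 35.4, which is 35.4/172.4 = 20.5% of the new diseased group. Set q = 1 − specificity, using the planning specificities of 94% and 87%.

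- 80%/94% test: (0.80 × 137 + 0.06 × 35.4)/172.4 = 64.8%. With q = 50% it is 73.8%.
- 65%/87% test: (0.65 × 137 + 0.13 × 35.4)/172.4 = 54.3%.
- The 15-point design difference becomes 64.8 − 54.3 = 10.5 points.

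Over k = 10 to 49 (49 being 10% of 491), again with q = 1 − specificity, 80% becomes 75.0% to 60.5%, and 65% becomes 61.5% to 51.3%.

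**Index-triggered FFA.** The triggering test is positive in the eye by definition, so q = 1 for it. Take k = 20, with q = 1 − specificity for the other test.

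- Triggered by the 65% test: it becomes (89.05 + 20)/157 = 69.5%; the 80% test becomes (109.6 + 1.2)/157 = 70.6%. The difference falls to 1.1 points.
- Triggered by the 80% test: it becomes (109.6 + 20)/157 = 82.5%; the 65% test becomes (89.05 + 2.6)/157 = 58.4%. The difference widens to 24.1 points.

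A rise is limited by the false positives available: 0.06 × 354 ≈ 21 for the 80%/94% test (so k up to about 26) and 0.13 × 354 ≈ 46 for the 65%/87% test (k up to about 70). With q from 1 − specificity to its feasible maximum and k from 10 to 49, the change runs from about −20 to +8 points.

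**Adding the index recode in Table 4.** Eight-weekly visits over three years give about 19 (156/8 = 19.5). Under the any-positive collapse, and assuming independent visits, a participant otherwise negative throughout becomes index-positive with probability 1 − (1 − p)^19: 31.9% at p = 2% per visit and 86.5% at p = 10%.

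Apply this to the 80% test with k = 35.4 and q = 6%, giving everyone 19 visits:

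- p = 2%, 0.98^19 = 0.681: [137(1 − 0.20 × 0.681) + 35.4(1 − 0.94 × 0.681)]/172.4 = 76%.
- p = 10%, 0.90^19 = 0.135: the same formula gives 95%.

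So the FFA recode alone gives 65%; adding the index recode gives 76% or 95%. The two recodes pull in opposite directions here and cannot be separated in the SA5 output.

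**Under a final-FFA rule.** The k eyes stay reference-negative and contribute no change in sensitivity.

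**The case against.** The strongest reply is that A1 uses one final FFA and the sensitivity analyses follow A1, so the later negative result stands and nothing is relabelled. That reading is available, and it makes the defect partly one of contradiction. It does not override the text: the any-time rule is the definition printed for Table 4 and recurs in the Method paragraph, Table 2 and the McNemar construction, while the last-FFA list governs inclusion rather than disease status. In the default data the two rules should usually agree because follow-up ends at diagnosis; SA5 is where they separate.

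A second reply is that the SAP's stated assumption is general (indeterminate means missing), so recoding every indeterminate result tests it directly. That is fair as far as the wording goes. But where a later definite FFA exists, the assumption has no bearing on A1, so overriding that result says nothing about A1's dependence on it.

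A reader might infer that SA5 always lowers sensitivity. The documents do not support this: unscheduled study FFAs are triggered by positive index tests, and Table 4 recodes index results too, so sensitivity can rise. A reader might also infer that the primary estimates are fragile or wrong. A1 is untouched, and SA5 is a conditional extreme case paired with SA6. Nor do the documents show that resolved eyes would dominate SA5, since they give no indeterminate rates.

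Limiting the index recode to the last visit may also seem a natural remedy. It would break the any-visit collapse that SA5 shares with A1, so I do not propose it.

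**Conclusion.** The point holds as a defect in SA5. As printed, it relabels as nAMD eyes that a later definite FFA showed to be negative, and the SAP's two descriptions of the reference standard leave this unresolved. The shift is artificial and specific to each test. On assumed rates it takes 80% to about 65% when 35 eyes are relabelled, 6% are test-positive and no index results are recoded; it is upward for a triggering test, or with enough index recoding. The paired differences can shrink or widen by an amount comparable with the 15-point design difference. All of this rests on assumed values of k, q, p and the number of visits. The consequence is confined to a conditional sensitivity analysis, so this should be corrected but does not threaten the primary result.

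**What to change.** In the Sensitivity analyses text and in Table 4:

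1. State that SA5 and SA6 recode an indeterminate local FFA (positive in SA5, negative in SA6) only when the participant has no later definite local FFA, and that a later definite result otherwise stands.
2. Reconcile the text, which recodes FFAs only, with Table 4, which recodes FFAs and index tests.
3. Report the FFA recode separately from the index-test recode, so that the effect of each can be seen.
4. Align the single-final-FFA description of A1 with the any-time definition in Table 2 and above Table 4, and give the denominator for the 10% condition.

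The cost is a few sentences in the SAP and an extra set of SA5/SA6 output tables. No new data are needed, and A1 is unchanged.
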